According to the results of large trials of septic shock treatment, the 90-day mortality was 30% in the usual-care group.⁹⁻¹¹ Based on this information, we calculated that a sample of 254 patients would have a power of 80% to detect a relative reduction of 50% in risk (15 percentage points of absolute risk reduction) in the UGFM group, allowing for a loss to follow-up or withdrawal of 5%. The target number for primary outcome analysis would be 121 patients per

group. One interim analysis was performed after the enrollment of 50% of the patients, with the use of a two-sided symmetric O'Brien–Fleming (or alpha spending method) design.

Statistical analysis

We used Stata version 14.0 (StataCorp LLC, College Station, TX) for all statistical tests and production of graphics. The normally and non-normally distributed data were analyzed using the two independent-samples t test and Mann-Whitney U test, respectively. A χ^2 test with odds ratio (OR) was performed to compare the proportions between the groups. No data were imputed for any missing information. We used the Kaplan-Meier curve and the log-rank test to compare the 30-day mortality between the treatment arms. All tests were two-sided for superiority testing and considered statistically significant at a $p < 0.05$.

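### 30-day mortality and 72-hour SOFA change are compared without baseline covariates; pre-specified adjustment for hour-0 SOFA and lactate is an optional precision gain, not the repair of an error

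*Combined protocol and SAP*

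**What the plan says.** The Statistical analysis section gives three rules for comparing the arms:

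- Continuous outcomes: "The normally and non-normally distributed data were analyzed using the two independent-samples t test and Mann-Whitney U test, respectively".
- Proportions, which would include the proportion dead at 30 days: "A χ^2 test with odds ratio (OR) was performed to compare the proportions between the groups".
- Survival: "We used the Kaplan-Meier curve and the log-rank test to compare the 30-day mortality between the treatment arms".

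No regression, ANCOVA, Cox model or stratified test appears. On missing data the section says: "No data were imputed for any missing information".

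The baseline values are nevertheless part of the plan. The Study Protocol section lists blood lactate among the items collected at hour 0. Outcome Measurements takes lactate again at six hours, and scores SOFA at 72 hours as a change from hour 0. Randomisation is 1:1 in permuted blocks of four, with no stratification factor described.

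Sample-size determination assumes that "the 90-day mortality was 30% in the usual-care group" and that UGFM halves it to 15%. It states: "The target number for primary outcome analysis would be 121 patients per" group, with 254 enrolled. It also reports: "One interim analysis was performed after the enrollment of 50% of the patients", with an O'Brien-Fleming design.

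**The concern.** Hour-0 SOFA and lactate are severity measures that may well predict death and later SOFA. Neither the randomisation nor the analysis uses them as covariates. The SOFA change score does use the baseline, but fixes its weight at 1 instead of estimating it.

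The design reaches 80% power only for a halving of mortality, so there is little to spare. The 30% planning risk is a 90-day figure while the analysis is at 30 days. If the 30-day risk is lower and the relative effect is the same, unadjusted power falls further. Adjustment could recover some of that without another patient or measurement.

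**Working it through.** **1. The plan's own figure.** Inputs from Sample-size determination: 30% v 15%, 80% power, 5% loss. From Statistical analysis: two-sided 0.05.

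n per group = [1.960·√(2·0.225·0.775) + 0.8416·√(0.30·0.70 + 0.15·0.85)]² / 0.15² = (1.1575 + 0.4889)² / 0.0225 = 120.5, so 121. The total is 242/0.95 = 254.7 or 242 × 1.05 = 254.1; the stated 254 agrees within rounding. Exact chi-square power at 121 per group is 80.9%. The stated size is correct and does not depend on adjustment.

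**2. Mortality.** The documents give no prognostic strength, so the AUC is assumed. Method: 40,000 simulated trials per setting, 121 per arm, and two baseline covariates (assumed correlation 0.4) whose sum has the stated AUC in the control arm. Logistic regression uses a likelihood-ratio test. Cox uses a Wald test, under proportional hazards with censoring at day 30. Power (%) at 30% v 15%, with gains taken before rounding:

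| AUC | Chi-square | Logistic | Gain | Log-rank | Cox | Gain |
|---|---|---|---|---|---|---|
| 0.50 | | | -0.1 | | | -0.8 |
| 0.60 | 81.0 | 81.8 | 0.8 | 80.8 | 80.9 | 0.1 |
| 0.65 | 81.0 | 82.8 | 1.8 | 81.0 | 82.2 | 1.3 |
| 0.70 | 81.1 | 84.4 | 3.4 | 81.0 | 84.3 | 3.3 |
| 0.75 | 80.7 | 86.5 | 5.8 | 81.0 | 87.2 | 6.1 |
| 0.80 | 80.6 | 89.2 | 8.7 | 81.4 | 91.3 | 9.9 |

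Type I error at AUC 0.70 (30% v 30%) is 4.8 to 5.3% for all tests, with or without the interim look. The standardised risk difference has power within 0.2 point of logistic regression.

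**3. Lower 30-day risk.** Gains in points at AUC 0.60/0.70/0.80:

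- 25% v 12.5% (exact chi-square power 71.6%): logistic 0.9/3.7/8.9; Cox -0.1/2.8/10.7.
- 20% v 10% (59.7%): logistic 0.9/3.5/9.1; Cox -1.1/1.9/9.7.

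A further run at 20% v 10% gave log-rank 59.6% v Wald Cox 57.7% at AUC 0.50, a loss of 1.9 points. At AUC 0.60 it gave 58.9% v 57.8%, a loss of 1.1. The Wald Cox test can therefore lose power even when the covariates carry some information.

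**4. SOFA change.** Let ρ be the correlation between hour-0 and 72-hour SOFA, and k the ratio of their SDs (both assumed). The variance of ANCOVA relative to the change score is (1 - ρ²)/(1 + k² - 2ρk).

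- k = 1: this is (1 + ρ)/2 = 0.65/0.75/0.85/0.95 at ρ = 0.3/0.5/0.7/0.9. If the change score has 80% power, ANCOVA has 93.5/89.9/86.0/82.0%.
- k = 0.75: 0.82/0.92/0.995/0.89. For example, at ρ = 0.7 it is 0.51/0.5125.

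The reduction is thus 0.5 to 35%.

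Deaths before 72 hours complicate this. Assume 10% v 5% die by then and are ranked worst (k = 1, same ρ values, 10,000 trials per setting). Mann-Whitney on change then has 80.0/79.6/80.8/79.0% power, against 88.7/84.9/83.0/79.1% for the same ranks adjusted for hour-0 SOFA. With the same death rates and no true SOFA effect, a survivors-only ANCOVA shifts 0.02 to 0.07 SD against UGFM. The change score shifts 0.01 to 0.05 SD.

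**5. Missing baselines.** At AUC 0.70, with an assumed 5% or 10% of baselines missing, complete-case logistic power falls from 84.4% to 82.6% or 80.4%. Filling with the pooled mean keeps 84.2% or 84.1%.

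**6. Interim look.** At AUC 0.70 with the O'Brien-Fleming look at half, power is 80.5% (chi-square) v 84.2% (logistic), and 80.7% (log-rank) v 83.9% (Cox). With an unadjusted interim and an adjusted final test, power is 84.2% or 84.0% and type I error 5.1%.

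**The case against.** The strongest objection is that nothing is broken. The unadjusted tests are valid in a randomised trial, and the design reaches its stated power without covariates. That stands. A reader might infer that the plan is in error or the trial too small; step 1 of the working shows otherwise.

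The second is timing. The document is dated 1 October 2020, is written in the past tense and reports the interim as done. That also stands: adjustment chosen after the arms have been compared is not pre-specified.

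The third is that every gain rests on assumed inputs and may be near zero or negative. That stands as a limit on size. A reader might infer that the worst loss is about 1 point and arises only with useless covariates. The results at 20% v 10% do not support that for the Wald Cox test.

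Two other readings go too far:

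- **Lactate clearance.** One might infer a comparable precision gain. The clearance formula is not given, and no gain can be computed from the documents.
- **Chance imbalance.** One might treat it as a separate flaw. At 121 per arm, the SD of the standardised difference is √(2/121) = 0.129, so a difference above 0.2 SD has probability 0.12. The unadjusted test's error rate and confidence interval already allow for this; it is the lost precision seen another way.

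The point also does not extend to fluid volume, renal replacement or ventilation.

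**Conclusion.** The point holds as an optional improvement. The plan leaves unused, as covariates, two baseline measures that it already needs. For mortality, the benefit is negligible if they predict death weakly, and worthwhile from an AUC of about 0.70. For SOFA change it ranges from almost nothing to about a third of the variance. All of this depends on the assumed AUC, ρ, k and early-death rates. Logistic regression carried almost no penalty in the settings simulated (at worst -0.1 point). The appreciable losses were with the Wald Cox test; likelihood-ratio and score versions were not simulated. If the arms have been compared, what remains is a supportive analysis that helps readers judge baseline imbalance.

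**What to change.** Before the arms are compared:

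1. Keep the 30-day endpoint and the log-rank test. Add one adjusted mortality analysis on hour-0 SOFA and log hour-0 lactate. Use either logistic regression reported as a standardised risk difference with 95% CI, or Cox regression with a likelihood-ratio or score test. State which mortality analysis is primary.
2. Analyse SOFA change with hour-0 SOFA as a covariate. Use ANCOVA, or an adjusted rank analysis if deaths before 72 hours are ranked worst. The latter makes the outcome a death/SOFA composite and must be labelled so. Do not rely on a survivors-only ANCOVA.
3. Fill missing hour-0 covariates with the pooled mean, as the only exception to the no-imputation rule. No patient with an observed outcome is then dropped by the adjustment. Outcomes stay unimputed.

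An analysis of log 6-hour lactate adjusted for log hour-0 lactate may be added, without a claimed gain. The rule for early deaths, the clearance formula and the timing of hour-0 sampling relative to treatment are separate details that also need stating.

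If the arms have already been compared, label these analyses post hoc and supportive.

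The cost is a few lines of SAP and Stata code, with no new data if hour-0 SOFA is recorded as the change score requires. The covariates and effect measure must be fixed in advance. An adjusted odds or hazard ratio is a conditional measure, so it does not estimate the same quantity as the unadjusted ratio.

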Patients were promptly treated with 30 mL/kg loading of NSS in this treatment arm. After the NSS bolus, treatment with either the additional IV fluid or a vasopressor was given at the physicians' discretion during the six-hour study period. The threshold for the need of a vasopressor was set at mean arterial pressure below 65 mm Hg if a patient did not respond to fluid therapy during each treatment protocol, and the time of vasopressor administration was noted. However, ancillary fluid administration was allowed at treating physicians' judgment in both treatment arms. Other adjunctive therapies, such as colloid administration, central venous catheterization, or surgical removal of the infectious source, were not prohibited in our protocol and were used at the discretion of the treating physicians. The study patients were closely monitored while we recorded their clinical parameters every two hours for study purposes. Our resuscitative study protocol stopped at six hours after initiation of the treatment. After this period, patients were treated according to the physicians' judgment.

Outcome Measurements

At six hours after treatment, the cumulative fluid volume was recorded, and blood lactate was obtained for lactate clearance calculation. At 72 hours after ED presentation, the cumulative fluid volume from the initial presentation was again recorded, and the patients were followed for clinical condition evaluation and blood chemistry tests to calculate the SOFA score and assess its change from the hour-zero baseline. The in-hospital requirement and time to start renal replacement therapy or MV were followed and recorded by searching the electronic data summary of a patient. The indication to initiate these life-saving procedures was at the discretion of the treating physicians. To identify the deceased patients for mortality analysis, we retrieved the electronic database of in- and outpatient clinical records or made a telephone call to the patients or their personal contact in every case at 30 days after the day of hospital presentation. The clinical data retrieval was performed and recorded by the trained non-investigators.

Data Analysis

Sample-size determination

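### No rule is stated for deaths before 72 hours, so by default the 72-hour SOFA change is compared only in patients alive and assessed then, which is not a comparison of the randomised groups

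*Combined protocol and SAP*

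**What the plan says.** Outcome Measurements defines the 72-hour assessment: patients are followed for clinical evaluation and "blood chemistry tests to calculate the SOFA score and assess its change from the hour-zero baseline". A 72-hour cumulative fluid volume is recorded at the same time. In the same section, deaths are identified for the mortality analysis, by record search or telephone at 30 days. Nothing links them to the SOFA score.

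Data Analysis, Statistical analysis, gives the tests: "The normally and non-normally distributed data were analyzed using the two independent-samples t test and Mann-Whitney U test, respectively". The only statement on missing data is "No data were imputed for any missing information". Mortality has its own analysis: "We used the Kaplan-Meier curve and the log-rank test to compare the 30-day mortality between the treatment arms".

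Sample-size determination starts from 30% mortality at 90 days under usual care and plans to detect "a relative reduction of 50% in risk (15 percentage points of absolute risk reduction) in the UGFM group". It allows 5% for loss or withdrawal and arrives at 121 evaluable patients per group. It also reports that "One interim analysis was performed after the enrollment of 50% of the patients".

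The documents give no worst score, rank, composite outcome, estimand or sensitivity analysis for patients who die before 72 hours. They also give no rule for patients alive at 72 hours without a score.

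**The concern.** A patient who dies before 72 hours has no 72-hour SOFA. With nothing imputed and tests that run on observed values, that patient drops out of the comparison. Survival to 72 hours comes after randomisation and may itself depend on treatment, so the patients left in the two arms need not be comparable.

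The comparison is biased if early death is related to the course of SOFA and if either the early death rate or that relation differs between arms. Equal early mortality is therefore not enough to guarantee an unbiased result.

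This is a population with sepsis-induced hypoperfusion or septic shock, and the trial is planned on a halving of mortality. If some of that reduction falls before 72 hours, usual care loses more of its sickest patients from the SOFA comparison than UGFM does. Readers would take the resulting p-value as a randomised comparison of organ failure when it is conditional on survival.

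**Working it through.** **The plan's own figure.** For 30% v 15%, two-sided 5% and 80% power, with average proportion 0.225:

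n = [1.96·√(2·0.225·0.775) + 0.842·√(0.30·0.70 + 0.15·0.85)]² / 0.15² ≈ 121 per group.

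This matches the plan. Allowing 5% loss, 242/0.95 gives 255 against the stated 254. The figure concerns mortality only; no figure is given for SOFA.

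**Assumed inputs (not in the documents).** Baseline SOFA B is normal with mean 8, SD 3. The change C to 72 hours is independent and normal with mean −2, SD 3.5. The death model is logit P(death by 72 h) = a + b(B + C), with b = 0.2 or 0.35. The 30% and 15% are 90-day planning figures, so early death rates were varied.

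**Formula.** Mean change in survivors = E[C·(1 − P)] / E[1 − P], by numerical integration. The intercept a is set so that each arm has its stated early death rate.

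**(a) Same slope in both arms, early deaths halved in UGFM, no SOFA effect.** The true difference is 0; a positive shift means UGFM looks worse.

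| Early deaths, usual care / UGFM | Survivor mean change, b = 0.2 | Shift | Survivor mean change, b = 0.35 | Shift |
|---|---|---|---|---|
| 6% / 3% | −2.14 / −2.07 | +0.07 | −2.21 / −2.11 | +0.10 |
| 10% / 5% | −2.23 / −2.12 | +0.11 | −2.34 / −2.18 | +0.16 |
| 15% / 7.5% | −2.33 / −2.17 | +0.16 | −2.49 / −2.26 | +0.22 |
| 20% / 10% | −2.43 / −2.23 | +0.21 | −2.63 / −2.34 | +0.29 |

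At 121 per arm the standard error of the difference is about 3.5·√(2/121) = 0.45 points. The shift is thus 0.07/0.45 to 0.10/0.45, or 16–22% of a standard error, at 6%/3%. At 20%/10% it is 0.21/0.45 to 0.29/0.45, or 47–64%. Over wider inputs (change SD 2.5–4.5, slope 0.1–0.5, same early death rates) the shift runs from 0.02 to 0.49 points.

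**(b) A true 1-point benefit that affects early death only through SOFA.** Early deaths fall from 6% to 4.5–5.0%, or from 20% to 16–17%. The benefit then appears as 0.95–0.98 or 0.89–0.95 points.

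**(c) Equal early deaths (6% to 20%) but different slopes, no SOFA effect.** Slopes of 0.2 v 0.35 give 0.08–0.19 points in favour of the arm with the steeper slope. Slopes of 0.1 v 0.5 give 0.19–0.50.

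**(d) Early deaths halved and a steeper slope in UGFM, no SOFA effect.** With 0.2 (usual care) v 0.35 (UGFM) the shift is still against UGFM: +0.03 at 6%/3% and +0.10 at 20%/10%. Only with 0.1 v 0.5 does it favour UGFM, by 0.07 and 0.17.

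**Rejection rate with no SOFA effect and deaths halved** (Mann-Whitney, two-sided 5%, 6,000 simulated trials per scenario). The observed-value test rejects 5–6% of the time at 6%/3%, 6–7% at 15%/7.5% and 7–10% at 20%/10%.

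**Fluid volume.** For each 1 L by which recorded volume differs between dying patients and survivors, dropping those patients instead of counting to death moves the arm difference by (0.06 − 0.03)·1 = 0.03 L, or (0.20 − 0.10)·1 = 0.10 L.

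**The case against.** **The survivor comparison is inferred.** A reader might infer that the plan prescribes a survivors-only SOFA analysis. It does not; the Statistical analysis section never mentions SOFA. What stands is that a missing value, no imputation and tests on observed values lead there by default.

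**The effect is small.** At 6%/3% the shift is about a fifth of a standard error and the test keeps close to its nominal level. Visible inflation needs 15–20% of usual-care patients dead within 72 hours, which is half to two-thirds of the 30% assumed by 90 days. This stands and limits the weight of the point.

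**The direction is mostly conservative.** A reader might infer that the gap could readily manufacture a SOFA benefit for UGFM. With deaths halved, that needs strongly different slopes between arms, and nothing in the documents suggests them. With equal early deaths a slope difference alone can push either way, but the documents do not suggest that difference either.

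**Ranking deaths worst is not plainly better.** It answers a different question and partly re-tests mortality. With no SOFA effect and deaths halved it rejects 5–6% of the time at 6%/3%, 10–11% at 15%/7.5% and 14–18% at 20%/10%. With a 1-point benefit and equal early deaths its power is about 48–50% against 56–57% at 6%, and roughly 30% against a little over 50% at 20%. Where the benefit acts only through SOFA it gains essentially nothing. This stands: the ranked test belongs beside the planned comparison, not in its place.

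**Ranking deaths does not cover everyone.** Living patients without a 72-hour score also lack a value and need their own rule. This stands too.

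**Conclusion.** The gap is real. As written, the 72-hour SOFA comparison rests by default on patients alive and assessed at 72 hours and is not protected by randomisation. That is a matter of what the result can be said to show, and it holds whatever the size of the bias.

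The size cannot be derived from the documents. Under the assumptions above, with early deaths halved in UGFM, UGFM looks worse by 0.07–0.10 points at 6%/3%, 0.16–0.22 at 15%/7.5% and 0.21–0.29 at 20%/10%, the last being an upper extreme. The bias is small unless early deaths are many. Where UGFM has fewer early deaths it usually understates a UGFM benefit.

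A reader might go further and doubt the mortality result. The documents do not support that: deaths are analysed directly by Kaplan-Meier and log-rank, and the sample size was set on mortality, not SOFA. The handling of 72-hour fluid volume in patients who die early is a clarification only. The point should be addressed; confidence in its size is medium.

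**What to change.** Add to the Statistical analysis section:

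1. Report by arm the number of deaths before 72 hours and the number alive but not assessed at 72 hours.
2. Keep the observed-value SOFA comparison, labelled as conditional on survival to 72 hours and not a comparison of the randomised groups.
3. Add, as a companion sensitivity analysis and not a replacement, a Mann-Whitney test in which deaths before 72 hours rank worse than any survivor. Describe it as a combined death and organ-failure comparison, and state a rule for living patients with no 72-hour score.
4. Label these additions post hoc if outcome data have already been seen. The plan is written in the past tense and reports an interim analysis, so this must be settled.

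As a clarification, state whether 72-hour fluid volume in patients who die earlier is counted to death or excluded.

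The cost is wording and a little more analysis; the planned Kaplan-Meier curve already needs death times. The downside of item 3 is that the ranked test partly repeats the mortality comparison and loses power for SOFA when early deaths are equal, which is why it should not lead.

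### Does the single p < 0.05 threshold, with no level written for either look of the O'Brien-Fleming design, leave type I error uncontrolled?

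*Combined protocol and SAP*

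**What the plan says.** Sample-size determination: "One interim analysis was performed after the enrollment of 50% of the patients", using a "two-sided symmetric O'Brien–Fleming (or alpha spending method) design". No boundary, nominal p-value or amount of alpha spent is given for the interim or the final look, and the parenthesis leaves two methods open.

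Statistical analysis: "We used the Kaplan-Meier curve and the log-rank test to compare the 30-day mortality between the treatment arms". The next sentence closes the plan: "All tests were two-sided for superiority testing and considered statistically significant at a $p < 0.05". It makes no exception for the mortality comparison and does not say whether 0.05 is the overall level or the level for the last test.

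Outcome Measurements: survival status is ascertained "in every case at 30 days after the day of hospital presentation". The sample size, by contrast, rests on a 90-day figure: "the 90-day mortality was 30% in the usual-care group".

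**The concern.** A group-sequential design holds its overall error rate only if the final test uses the design's own final level, which is below 0.05 once some alpha has been set aside for the interim. Here the one printed threshold covers every test and comes straight after the log-rank test of mortality. A reader could conclude that the final mortality test will be judged at an unadjusted 0.05, so that alpha exceeds 5%.

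The two named methods also differ at the end: 0.0480 against 0.0490 at half information. A final p-value of 0.0485 would fail under one and pass under the other. A value of 0.0495 would fail under both and pass under 0.05. At stake is whether a result in that narrow band counts as positive, with the answer not printed in advance.

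**Working it through.** **Inputs.** Sample-size determination gives 30% mortality under usual care, a 15-point absolute reduction (so 15% under ultrasound guidance), 80% power, 5% loss, 121 per group for analysis, 254 in total, and one interim at 50% enrolment. Statistical analysis gives two-sided 0.05. Assumption: information is proportional to patients, so the information fraction is t = 0.5; lower values are tried below.

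**1. The plan's own sample size.** With pooled variance under the null and mean rate 0.225:

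n = [1.960 × √(2 × 0.225 × 0.775) + 0.842 × √(0.30 × 0.70 + 0.15 × 0.85)]² / 0.15² = 120.47, so 121 per group.

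The total is 242 × 1.05 = 254.1, against 254 stated. A fixed two-sided 5% test therefore reproduces both figures, and 0.05 is the level on which the whole trial was sized.

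**2. Levels implied by the named design.** Under the null, the two test statistics are bivariate normal with correlation √t = 0.707. The boundaries solve P(|Z1| ≥ c1 or |Z2| ≥ c2) = 0.05.

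- Classic O'Brien-Fleming, c1 = c2/√t: c2 = 1.977 and c1 = 2.797, so p = 0.0052 then 0.0480.
- O'Brien-Fleming-type spending, 0.025 per side: interim spend 4 × [1 − Φ(2.241/0.707)] = 0.0031, so c1 = 2.963 and c2 = 1.969, giving p = 0.0031 then 0.0490.
- The same spending function applied to a single two-sided 0.05: 2 × [1 − Φ(1.960/0.707)] = 0.0056, then 0.0478 at the end.

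The plausible final levels run from 0.0478 to 0.0490.

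**3. Overall alpha if the boundary is kept at the interim and 0.05 (|Z| ≥ 1.960) is used at the end.**

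| Information at interim | Classic | Spending (0.025 per side) |
|---|---|---|
| 50% | 5.20% | 5.10% |
| 40% | 5.08% | 5.03% |
| 30% | 5.01% | 5.00% |

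The lower rows are relevant because mortality is read at 30 days, so a look triggered by enrolment may hold less than half the information. In the other direction, 127 enrolled out of 242 analysed, all informative, gives t = 0.525 and 5.23% (classic).

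**4. Overall alpha if 0.05 is used at both looks.** At t = 0.5 it is 8.31%.

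**5. Effect on the trial's verdict.** A log-rank simulation (400,000 trials, 121 per arm, exponential times censored at 30 days, interim on the first 122 patients with full follow-up) compared a final 0.05 with the design's final level. With 30% mortality in both arms, rejection was 5.25% against 5.04% (classic) and 5.15% against 5.05% (spending). At 30% against 15% mortality, the verdict differed in 0.47% (classic) or 0.23% (spending) of trials.

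**6. Power.** Over two looks, power at 121 per group is 80.0% under spending and 79.8% to 79.9% under classic O'Brien-Fleming. Using the boundary does not disturb the sample size.

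**The case for a change.** The strongest case for a change is that a plan should fix its decision rule before the data are seen, and this one names two methods and chooses neither. Even if 0.05 is the overall level, the choice between 0.0480 and 0.0490 stays open. Read to the letter, the threshold for every test also reaches the interim, which would give 8.31%. Printing two numbers would cost a few words.

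Part of this stands. The levels are not printed, the choice of method is not closed, and 5.2% is not a ceiling on every reading. But the 8.31% reading requires ignoring the boundary that the plan names for that very look. The intermediate reading, with the boundary honoured at the interim and dropped at the end, takes half of a design that is defined as a pair of boundaries holding one overall level. The ordinary reading uses both sentences: 0.05 is the overall level and the named design divides it.

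The amendment is also less simple than it looks. The plan does not say which test the interim design governs. It sizes on 90-day mortality, lists a χ² test for proportions and a log-rank test for 30-day mortality, and does not name the primary outcome. Attaching levels to one of these would settle a separate question. And the plan speaks of the interim in the past tense; if that is literal, a boundary chosen now would not be pre-specified.

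**Conclusion.** The concern does not call for a change. This is a gap that analysts fill sensibly: one interim, half enrolment, two-sided symmetric O'Brien-Fleming and an overall 0.05 determine the per-look levels to within about 0.001 at the final look (0.0478 to 0.0490 across the plausible variants at 50% information).

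On the unfavourable but still plausible reading, with the boundary at the interim and 0.05 at the end, the excess alpha is 0.1 to 0.2 percentage points at 50% information and between 0.00 and 0.08 at 30% to 40%. The verdict would change in about 0.2% to 0.5% of trials under the design alternative, and only for a final p-value just below 0.05. Sample size and conduct are unaffected.

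This rests on three assumptions: the named design governs the interim look; information is roughly proportional to patients with known outcome; and the interim can support an efficacy claim, which the plan does not state. If it cannot, there is no inflation from the final 0.05 at all.
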